5. STUDY DESIGN

5.1 OVERALL DESIGN

The design for this study is a pilot, open-label clinical trial which will be used to investigate the preliminary efficacy of closed-loop alpha-tACS for the treatment of depression. We are recruiting from a clinical population. Participants will be up to 35 people ages 18-70 with unipolar, non-psychotic MDD, who have a HDRS-17 > 8 and are at a low risk for suicide according to the Columbia Suicide Severity Rating Scale (C-SSRS). Nursing and pregnant participants will be excluded from participation, and all women of child-bearing potential will be required to use an appropriate form of birth control throughout their participation. These individuals will be outpatients and may or may not seek or receive concurrent mental health care from a family practitioner, therapist, or psychiatrist.

This is a single-site, pilot clinical trial with a single arm. We will use the XCSITE100Pro stimulator designed by Pulvinar Neuro for investigational purposes to deliver closed-loop stimulation over five consecutive days. Participants will stay in a relaxed yet experimentally controlled state by watching a nature movie such as "Reefscape" during stimulation. The initial session (D1) and D5 will take approximately 2 hours. D2-D4 will take 1 hour. The 2-week (FU2) and 6-week (FU4) follow-up will take

approximately 1 hour. Completion of patient-administered surveys at FU1 to FU7 will take about 30 minutes to complete. We estimate that total participation to be approximately 13 hours.

5.2 Scientific Rationale for Study Design

This study is an open-label pilot interventional study. Given the novelty of the treatment and the absence of data to estimate effect sizes, an initial open-label trial is warranted.

5.3 JUSTIFICATION FOR DOSE

We are utilizing the same dosage as given in a similar pilot study: 5 consecutive days of up to 40-minutes of stimulation [6].

5.4 END OF STUDY DEFINITION

The end of this study is defined as when the last participant completes the final study visit (i.e., the last participant completes the FU7 study visit).

6. STUDY POPULATION

6.1 INCLUSION CRITERIA

In order to be eligible to participate in this study, an individual must meet all of the following criteria:

- Ages 18-70 years
- DSM-V diagnosis of MDD; unipolar, non-psychotic
- Hamilton Rating Depression Rating Scale (HRDS-17) score >8
- Low suicide risk as determined by the C-SSRS triage form (no intent or plan)
- Capacity to understand all relevant risks and potential benefits of the study (informed consent)

6.2 EXCLUSION CRITERIA

An individual who meets any of the following criteria will be excluded from participation in this study:

- DSM-5 diagnosis of severe alcohol use disorder (AUD) within the last 12 months
- DSM-5 diagnosis of moderate to severe substance use disorder (excluding tobacco) within the last 12 months
- Lifetime history of bipolar disorder, psychotic disorder, schizophrenia, autism
- Current use of benzodiazepines > 20mg diazepam/d equivalent
- Antidepressant dose change within the last 2 weeks
- Initiated new antidepressant within the last 4 weeks
- Initiated psychotherapy within the last 4 weeks
- Initiated other form of non-medication, non-neurostimulation treatment within the last 4 weeks
- Currently or history (3 months) of receiving TMS, ketamine, esketamine, or ECT.
- Previously failed to respond to ECT or TMS
- History of seizure (excluding febrile seizures in childhood or ECT induced seizures)

- Neurological disorders that would increase risk of participation or present a significant confounder in the opinion of the investigator (for example, dementia, history of stroke, Parkinson's disease, multiple sclerosis, history of traumatic brain injury with prolonged loss of consciousness, ruptured cerebral aneurysm, previous CNS radiation)
- Unstable medical disorder in the eye of the study physician
- Prior brain surgery and/or brain implants
- Current pregnancy or breastfeeding
- Unwillingness to use appropriate birth control if sexually active
- Currently enrolled in another clinical trial for depression
- Anything that, in the opinion of the investigator, would place the participant at increased risk or preclude the participant's full compliance with or completion of the study

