3.3.3 Assessment of Potential Risks and Benefits

The risks and benefits presented above are no more serious than for other clinical trials in this population. Based on the need for complementary and alternative treatments for MDD, the potential risks are worth the potential benefits. Furthermore, this is an open-label study that does not require considerations about the risks associated with a placebo group. We also note that the FDA has recently confirmed a non-significant risk (NSR) status for a very similar tACS trial in MDD.

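### The 3-month washout in section 6.2 omits transcranial electrical stimulation (tACS, tDCS), so recent or current users are eligible and could bias the single-arm change score in either direction

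*Combined protocol and SAP*

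**What the plan says.** All the relevant eligibility rules are in section 6.2.

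- Recent treatments carrying a 3-month interval: "Currently or history (3 months) of receiving TMS, ketamine, esketamine, or ECT".
- Other newly started treatments: "Initiated other form of non-medication, non-neurostimulation treatment within the last 4 weeks".
- Earlier non-response: "Previously failed to respond to ECT or TMS".
- Other trials: "Currently enrolled in another clinical trial for depression".
- Implants: "Prior brain surgery and/or brain implants".
- Investigator's discretion: anything that "would place the participant at increased risk or preclude" full compliance or completion.

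Section 4 defines the primary endpoint as the within-person HDRS-17 change between D1 and FU2. Section 10.4.2 tests it with a two-sided paired t-test, and section 10.4.1 pre-specifies no covariates. Section 7.4 names pharmacotherapy and psychotherapy as the therapies to be logged. Section 9.1 has screening record concomitant therapies, medical history and diagnoses, without mentioning earlier brain stimulation.

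**The concern.** The plan treats recent TMS or ECT as incompatible with a clean baseline, yet sets no interval for the modality it is testing. The 4-week rule sets neurostimulation aside, presumably because the 3-month rule was meant to cover it, and the 3-month rule then lists only two forms of it.

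With one open arm, no control group absorbs a carried-over effect. Section 10.2 itself relies on a tACS effect measured 2 weeks after treatment (dz = 1.58 for HDRS-17), so an effect still present at D1 is plausible on the plan's own evidence. The pre-stimulation EEG on D1, the reference for the exploratory alpha-power endpoint, is exposed in the same way. Section 5.2 justifies the open-label design by "Given the novelty of the treatment and the absence of data to estimate effect sizes". A change score that mixes first and repeat exposure serves that purpose less well.

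**Working it through.** **Step 1: apply section 6.2 to a person with recent or current tACS or tDCS.**

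- The 3-month rule does not apply, because neither method is listed.
- The 4-week rule does not apply, because it is confined to treatments that are not neurostimulation.
- The non-response rule does not apply, because it names only ECT and TMS.
- The implant rule does not apply, because tACS and tDCS are non-invasive.
- The other-trial rule applies only while the person is still enrolled elsewhere.
- The discretionary rule covers risk and compliance. Confounding is mentioned only in the bullet on neurological disorders.

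No criterion excludes a user outside a trial, or someone who has completed or left a trial.

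**Step 2: how wide the trial route is.** Take 3 months as about 13 weeks. The earlier trial in section 10.2 followed people to 4 weeks. For completers of a trial of that length, the gap runs from week 4 to week 13, about 9 weeks. For a trial with this study's 12-week follow-up it would be about 1 week. For someone who withdraws early, it opens at withdrawal.

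**Step 3: reproduce the plan's figures.** Exact paired t-test power (noncentral t, two-sided alpha 0.05):

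- dz = 1.58: power is 0.933 at n = 7 and 0.967 at n = 8, so the stated N = 8 for 95% power is right.
- dz = 0.55, n = 28: power is 0.801, matching the stated 80%.
- 28 / (1 − 0.20) = 35, matching the planned number consented.

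None of these is in dispute, and a change to eligibility does not alter them.

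**Step 4: illustrate the size.** The documents give neither the number exposed nor the size of any shift. I assume k = 1, 3 or 6 of 28 completers.

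- On the HDRS-17 scale, with each exposed person shifted by an assumed 5 points, the mean moves by k × 5 / 28.
- On the dz scale, with each shifted by an assumed 0.5 to 1.0 SD of change and the SD held fixed, dz moves by (k / 28) × shift.

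The plan gives no SD for the HDRS-17 change, so the two scales cannot be converted into each other.

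| k | Mean shift (points) | Shift in dz | Power at true dz 0.55, change shrunk | Power at true dz 0.55, change inflated | Rejection rate if true change is 0 |
|---|---|---|---|---|---|
| 1 | 1 × 5 / 28 = 0.18 | 0.018 to 0.036 | 0.775 to 0.747 | 0.825 to 0.848 | 0.051 to 0.054 |
| 3 | 3 × 5 / 28 = 0.54 | 0.054 to 0.107 | 0.717 to 0.618 | 0.868 to 0.918 | 0.059 to 0.085 |
| 6 | 6 × 5 / 28 = 1.07 | 0.107 to 0.214 | 0.618 to 0.403 | 0.918 to 0.974 | 0.085 to 0.194 |

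At dz = 1.58 power stays at about 1.00 in every row.

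**Step 5: direction.** Residual benefit at D1 lowers the starting score and shrinks the change. Relapse between D1 and FU2 also shrinks it. Continuing improvement from the earlier course inflates it.

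**The case against.** The strongest reply is that this is a drafting gap with few people behind it. Much of that stands. No document says how many applicants would have used tACS or tDCS. Entry requires HDRS-17 above 8, so someone still well after an earlier course does not qualify. The medical history taken at screening could bring exposure to light. In an uncontrolled pilot of preliminary efficacy, a few exposed people add modestly to an already large uncertainty. None of this closes the gap: a partly improved person can still score above 8, and a history that is not asked for may not be recorded.

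A reader might infer more than the documents support:

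- **That people come straight from this group's own tACS trials.** The current-enrolment rule largely blocks this. The one earlier trial described is cited to a 2019 paper, while the reference list includes 2021 papers, so its participants are well outside 3 months. Section 3.3.3 says the "FDA has recently confirmed a non-significant risk (NSR) status for a very similar tACS trial in MDD", but not whose trial that is or whether it has enrolled anyone.
- **That earlier responders would return and enrich the sample.** Nothing in the documents says so, and earlier tACS non-responders are equally eligible.
- **That the bias favours the treatment.** Two of the three mechanisms in Step 5 shrink the change.
- **That the response rate could rise by 11 to 21 percentage points** (3/28 and 6/28). If all exposed people respond, the rise is (k / 28) × (1 − p), where p is the response rate in the others. The full figures need p = 0. At an assumed p of 40% they are 6.4 and 12.9 points.
- **That anyone who was ever in a tACS depression trial should be excluded.** Carry-over does not justify a lifetime bar, which would be stricter than the plan's 3 months for having received TMS or ECT.

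**Conclusion.** The gap is real and follows from the wording of section 6.2: recent or ongoing tACS or tDCS meets no exclusion, and no section expressly asks about it. It could bias the primary change in either direction and could affect the D1 EEG baseline. Its size cannot be derived from the documents. On the assumptions shown, the shift is 0.18 to 1.07 HDRS-17 points. It is minor if one person is affected, material for effects near dz = 0.55 if several are, and without consequence for power at dz = 1.58. This does not invalidate the design. It is worth correcting because the correction is cheap and unrecorded exposure may not be recoverable later.

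**What to change.** 1. In section 6.2, add transcranial electrical stimulation (tACS, tDCS or similar) to the existing 3-month criterion. This uses the protocol's own interval. If the sponsor thinks another treatment of such exposure is warranted, the section should state it and give the reason.
2. Add one item on prior or current tACS or tDCS, with dates, to the electronic pre-screening survey, which already covers the eligibility criteria.
3. If anyone with such exposure is already enrolled, flag them and report the primary result with and without them. This is a sensitivity analysis and does not conflict with the decision in section 10.4.7 against demographic sub-group analyses.

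The cost is one phrase in section 6.2, one survey item, the IRB approval that any amendment needs, and a slightly smaller recruitment pool. Sample size, alpha and the primary test are unchanged.

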6.3 LIFESTYLE CONSIDERATIONS

People of child-bearing potential who are sexually active are asked to use an appropriate method of birth control.

6.4 SCREEN FAILURES

In the case that a participant does not qualify based on suicide risk, established procedures in the Carolina Center for Neurostimulation will be followed to ensure participant safety.

6.5 Strategies for Recruitment and Retention

This clinical trial will utilize multiple recruitment strategies to communicate this opportunity to as many potential participants as possible. First means is through a referral process. Participants can be referred to the study through their primary mental health care provider or family doctor during routine visits. This type of recruitment will take place in doctors' offices throughout Chapel Hill, Carrboro, Durham and Raleigh areas. Clinicians will be informed of inclusion criteria through email and listserv announcements and be asked to mention this clinical trial to appropriate patients and offer them a flyer/ brochure with contact information. We will also be using the UNC i2b2 to send request forms to the Carolina Data Warehouse to recruit participants who have been seen at UNC Hospitals that meet the inclusion criteria. ¹

In addition to referrals through primary care providers, we will advertise the study directly to the public websites such ClinicalTrials.gov, Research For Me, [name] on as and Carolinaneurostimulation.org. We will have contact information and a summary of the clinical trial posted on the [name] Lab Facebook and Twitter pages. Will we also be launching a Facebook or Instagram advertisement to identify potential patients. We will also use radio spots, newspaper ads, billboards, and in-person recruitment as needed. We will also be using the UNC Mass email and department listserv to send out an email that has the link to the survey. All patient identifiers will be stored in REDCap until recruitment is over. When recruitment is over, all patients who do not consent or are not eligible for participation in the study will have their responses permanently deleted in REDCap.

¹

We will send unencrypted emails to facilitate the initial contact to potential participants. Medical information is never requested per email. All medical information is recorded through HIPAA conform Zoom meetings and RedCap surveys.

Our retention strategy includes a payment schedule of three times per participant. The participant will receive payment in the form of a Visa Card at D1 (\$100). This card will be charged again on D5 (\$100), and the final follow-up session (\$100). Thus, completion of the study will result in a financial compensation of \$300.

Research personnel will be easily available for the participants to contact via email or phone. The inclusion criteria state that each participant must be able to understand all risks and benefits associated with this study. We will be asking each participant to answer questions about the consent form to determine that the study process and the duration of participation are completely understood by all participants. We will aim to have a specific research team member assigned to complete all sessions with the same participant. However, we will not require the same researcher to be present during stimulation sessions 2 through 4. The study team will work hard at forming rapport with the participant so they feel comfortable and willing to discuss what may be sensitive information. Retention will be quantified by the fraction of participants coming to each scheduled session (the data from each session will be scored and documented the day of the session).

As this study requires several days of participation in a row, we will allow participants to miss one stimulation session, if it is made up at the end of the stimulation week. If two consecutive stimulation sessions are missed, the participant will be withdrawn from participation. This schedule would permit the participant to still receive the full intervention (5 days of stimulation) without being withdrawn from the study due to unforeseen circumstances (e.g., inclement weather, car trouble).

7. STUDY INTERVENTION

7.1 Study Intervention(s) Administration

7.1.1 Study Intervention Description

We will be using the XCSITE100Pro stimulator designed by Pulvinar Neuro. The device is not implanted and has not been designed for or used to support or sustain human life. This device does not have a potential for serious risk to the health, safety, or welfare of the participant. There has never been an instance of serious side-effect reported due to the use of transcranial alternating current stimulation (tACS).

Previous studies in the [name] lab that used the XCSITE 100 and comparable devices (i.e., the commercial, CE-certified Neuroconn Plus stimulator) have been classified as "non-significant risk" by the full UNC IRB. The Neuroconn Plus stimulator and the XCSITE100 stimulator are electrically equivalent and provide the same stimulation. While the Neuroconn device is commercially available, it cannot be pre-programmed for closed-loop, and is not designed for tACS clinical trials. This makes the use of the Neuroconn device not appropriate for this study. The XCSITE 100 Pro includes identical stimulation hardware, including the safety features listed below, as the XCSITE 100.

The XSCITE100Pro stimulator may apply tACS for up to 40-minutes (2400 seconds) with appropriate current ramp-up at the beginning of stimulation and ramp-down at the end of stimulation. tACS may be applied for currents between 100 μ A and 8 mA (peak-to-peak for tACS). For the purposes of this study, this device will be set to deliver closed-loop tACS in the alpha frequency with a peak amplitude of 2 mA. For more instructions, please see the submitted instruction manual.

The stimulator includes the following safety features:

Current Sensor Circuit. A 33.2 Ω sense resistor is placed in series with the stimulation electrodes on the high side. Since high-side current sensing is used, any short circuit of the electrode terminals to ground will be detected. The stimulation current flows through this resistor and creates a voltage. The voltage across this resistor is sensed and amplified by the AD628 difference amplifier.

Voltage Sensor Circuit. The differential voltage across the electrodes is measured so that the impedance can be calculated. The voltage is measured by buffering the positive electrode and negative electrode each with a unity gain op-amp circuit. The voltage output is then shifted before it is read by the microprocessor using the same level shifting circuit described in the current sensor section.

The device is equipped with 4 different stages of safety precautions, all of which protect the participant from high currents. The stages are as follows:

- Automatic software current cutoff. The output of the current sensor described above is read by a
 microprocessor, which compares the reading to a value of +4 mA peak. If the current exceeds
 these limits, stimulation is turned off. The user is then given the option to investigate the issue,
 and cancel or resume the test. Since high-side current sensing is used (described above), any
 short circuit of the electrode terminals to ground will be detected.
- Automatic hardware current cutoff. The output of the current sensor is fed into a pair of comparators which detect if the current exceeds + 4.5 mA. If so, the fault is latched such that the relay in series with the electrodes is opened. Additionally, the microprocessor is notified of this instance through an interrupt. Upon this interrupt, the microprocessor immediately stops stimulation
- 3. *Permanent hardware current cutoff.* A 5 mA fast-acting fuse is in series with the electrode connector. If the above two over-current detection methods fail, the fuse will blow, and the stimulator will no longer be electrically connected to the device.
- 4. *Power supply fuse.* Finally, if for any other reason the entire device draws too much current, the main power supply fuse is triggered. This fuse is sized with a cutoff of 200% of steady-state operating current.

7.1.2 Dosing and Administration

The research team will first measure each participant's head using the 10-20 system to determine the electrode locations. Participants will then be fitted with the 3 electrodes for stimulation: two 5x5cm electrodes placed over F3 (left frontal cortex, standard 10-20 EEG coordinated) and F4 (right frontal cortex), and one 5x7cm electrode placed over C2 (midline, central). Electrodes will be carbon rubber, with Ten20 conductive paste applied. During stimulation, the participant will be in a relaxed and experimentally controlled state by watching a nature movie (such as Reefscapes). One session of stimulation will be performed per day, for up to 40-minutes. Before each stimulation session, a single-channel eyes open and eyes closed resting state EEG will be performed to individualize the treatment frequency.

The stimulation waveforms used in this study are tACS at the individual peak alpha frequency at 1 mA zero-to-peak amplitude both at F3 and F4, achieved via a splitter cable to distribute 2 mA between the two sites. Stimulation includes a ramp-in and ramp-out of 20 seconds, with a maximum of 40-minutes of stimulation at an amplitude of 1 mA per electrode, for a total of 2440 seconds of stimulation.

Research personnel will be thoroughly trained and have training documented on the transcranial stimulation device and will be present during all stimulation sessions. To monitor side effects of stimulation a stimulation effects questionnaire will be administered after each stimulation session. At D5, a systematic interview for side-effect is administered.

7.2 MEASURES TO MINIMIZE BIAS: RANDOMIZATION AND BLINDING

Randomization

There is no randomization since this is an open-label pilot study.

Blinding

There is no blinding since this is an open-label pilot study.

7.3 Study Intervention Compliance

Full compliance with the intervention is defined as completing all 5 daily stimulation sessions for 40 minutes each day. As the intervention is applied and monitored by research personnel, compliance can be directly observed.

7.4 CONCOMITANT THERAPY

Eligible participants will be permitted to be receiving concomitant therapy, such as psychotherapy, antidepressants, or other medications. However, eligibility for this trial includes a stable antidepressant medication dose for the past 2 weeks before the screening visits. Moreover, a new antidepressant must not be started during the last 4 weeks before the screening visit. Participants who are not taking medication for the treatment of MDD are also included.

To ensure that concomitant therapies are logged appropriately, participants will be requested to report any changes to the researchers. Furthermore, concomitant therapies (pharmacotherapy, psychotherapy) will be logged at Screening, D1, D5 and follow-up visit. Participants will be requested to include the dosing for these therapies (i.e., how often per day, how much in each pill, how many pills) as well as when they were first prescribed the medication.

